Visit 2: Fear Acquisition: Approximately 1 hr for all participants. Participants are considered enrolled in the study once they have begun Visit 2 (if enrolled in PTSD group, participant will be randomized). Visit 2 will occur within 6 months of Visit 1. If more than 6 months have passed, we will re-do Visit 1 before the participant is able to complete visits 2 – 5.

Visit 3: Fear Extinction: Approximately 5 hr for those receiving a capsule (PTSD groups) or approximately 3 hours for those not receiving a capsule (TEC group)

Visit 4: Fear Extinction Recall and Fear Renewal Test (approximately 24 hr after extinction, but no more than 1 week later): Approximately 1.5 hr

Visit 5: Fear Extinction Recall, Fear Renewal Test, & Debriefing (approximately 1 week after extinction, but no more than 3 weeks later): Approximately 1.5 hr

Nature of Participant Population: Participants of both genders will be included in the study and the age range of participants will be from 18-60. Persons below 18 or above 60 are excluded because beyond this range age may influence response to the drugs. Furthermore, the relatively small age range is intended to reduce variation in performance on the behavioral task. There are no enrollment restrictions based upon race or ethnic origin. Candidates will undergo a structured clinical psychiatric interview¹⁵⁰ and complete questionnaires related to their general physical health, current medications, with a detailed section on current and lifetime drug and alcohol use. This study will not involve vulnerable populations.

The number of participants expected to participate is 104: 78 trauma-exposed participants with PTSD and 26 trauma-exposed participants without PTSD (TEC; demographically matched). There will be 3 experimental groups: PTSD participants will be assigned to 5mg of THC (n=26), 10mg of THC (n=26), or a placebo (PBO) (n=26). The 26 TEC participants will not receive THC or PBO. With the conservative anticipation 25% will fail to complete all parts of the study, we estimate 20 PTSD participants in each condition (60 PTSD participants in total) and 20 TEC participants will complete the study for a total of 80 participants. Participants will be recruited from the Detroit community and mental health clinics. We will enroll up to 175 participants to guarantee enough viable data and to account for participant drop out.

Recruitment

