
Termination Criteria

Participants may be terminated for any of the following: (a) participant request to exit or withdraw consent; (b) development of risk of harm to self or others that requires immediate intervention; (c) alcohol, drug, medication use that would interfere with dronabinol or has level 1 evidence for severe drug-drug interaction with dronabinol; (d) development of a systemic, medical, neurologic, or psychiatric illness requiring treatment that would exclude participation; (e) clinical deterioration (see below); (f) non-compliance with study protocol requirements. We will make every effort to ensure that the sessions are accessible (i.e., scheduling sessions during evening and weekend hours). We will attempt to schedule Visits 2-4 on consecutive days, but in the event that this is not possible we will allow no more than 1 week between Visits 2 & 3 and Visits 3 & 4 and no more than 3 weeks between Visits 4 & 5. Of note, if there is more than 1 week between Visit 2 & 3, we will re-do Visit 2 and proceed with the rest of the visits as normal. But once a participant completes Visit 3, Visits 4 & 5 need to be completed within the above timeframe otherwise participation will be terminated. We will make every effort to ensure that appointments are accessible (i.e., scheduling an appointment during evening and weekend hours).

Medical and Neurological Health Determination

All health information collected in the pre-screening and baseline interview (Visit 1) will be reviewed by the PI or Co-I [name], who will indicate whether the participant is medically and neurologically healthy enough to continue in the study. These determinations may be made in person, over the phone, or via e-mail, and will be documented using a Medical Review form.

Emergent Suicidal or Homicidal Risk

The clinician or research staff may remove a participant from the clinical trial if the PI thinks that the participant is at imminent suicidal or homicidal risk. The presence of suicidal ideation is evaluated at the initial assessment. Endorsement of suicidal or homicidal ideation will be addressed in session. If the patient is deemed to have specific suicidal or homicidal ideation, the PI, Co-I [name], or Co-I [name] will be immediately notified and the participant will meet with the PI and/or Co-Is [name] and/or [name], or other licensed social worker/psychologist/psychiatrist covering for the PI or Co-Is on the premises, and the police will be alerted.

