Vulnerable Populations

This study will include women of child-bearing potential and college students. However, we will conduct urine pregnancy tests at the screening visit (Visit 1) and at the beginning of Visit 3 to make sure that women are not pregnant. Of note, if the participant is unable to provide a urine sample at Visit 1 (e.g., currently menstruating), we will conduct a urine pregnancy test at the beginning of visit 2. We will also conduct pregnancy tests if the study staff and/or participant have reason to believe they may be pregnant. In addition, participation of college students in this study is completely voluntary, as it is for all participants, and will not be required by any course.

Study Group Assignment

Individuals with PTSD will be randomized to a THC or PBO condition. In our previous studies we have shown that 7.5mg of THC facilitates extinction recall and modulates prefrontal and hippocampal activation in healthy humans volunteers^{55,113}. Moreover, PI [name] has preliminary data to suggest that 7.5mg of THC may facilitate extinction recall in PTSD, but it is not known whether this is the MED. This is an initial step in translation to be tested in the R61 phase. Therefore, we will have a low 5mg condition and a high 10mg condition should 5mg be too low to detect effects. Of note, a 10mg dose of THC does not typically produce anxiety¹⁵¹ or strong negative effects on cognition¹⁵². We aim to identify the MED that facilitates recall of extinction learning. Dronabinol is administered only by the oral route and will be placed in opaque capsules with dextrose filler. Placebo capsules will be identical in appearance but will contain only dextrose. All capsules will be administered to participants in double-blind conditions and participants assigned to receive dronabinol (two-thirds of the PTSD participants) will only receive dronabinol on one occasion.

Study medication, dronabinol or PBO, will be dispensed to participants by PI [name], who possesses a Schedule II-V controlled substance research license through the State of Michigan and the DEA and has experience in the use of dronabinol and PBO in human participant research. A registered pharmacist will handle

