The results of the breath alcohol test and urine drug and pregnancy tests performed at the beginning of Visit 3 (and Visit 1 for pregnancy test) will remain confidential. The only individuals who will have knowledge of the results of these tests are research staff directly working on the project. The breath alcohol and urine tests will be performed at the beginning of the visit. If the participant produces a positive pregnancy test at either Visit 1 or Visit 3 or reports becoming pregnant at any time during which they are active in the study, they will be withdrawn from the study at that time. At the beginning of Visit 3, if the participant (a) fails the alcohol breathalyzer test and/or (b) fails the urine drug test without any current medication use (e.g., non-illicit) which explains the positive result, the session will end at that time and the remaining visits will be rescheduled. Visits 3-5 will be rescheduled such that Visit 3 occurs within 1 week of Visit 2, otherwise the participant will need to re-do Visit 2. If the participant cannot be rescheduled or fails the urine drug test for a second time (i.e., at their rescheduled Visit 3) they will be withdrawn from the study. In the event of failed drug screen, follow-up questions will be asked to determine whether the result can be explained by a daily medication and not illicit drug use. This information will be stored in a secure computer database that uses participant codes (rather than names) as identifiers.

Other Tasks

Participants are re-assured that they can withdraw from the study at any time if they do not wish to experience the virtual snake. All participants will be informed that they are able to take a break at any time during any of the behavioral tasks.

Dronabinol

Participants are made aware of the side effects common to dronabinol in the informed consent document and again during their initial screening visit. Participants will be monitored for side effects at the pharmacological challenge visits. Participants are reassured that they can withdraw from the study at any time.

Magnetic Resonance Imaging

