A serious adverse event (SAE) is any severe adverse experience occurring during the study that: (a) results in death, (b) is life-threatening (e.g., suicidality, homicidality), (c) results in hospitalization or prolongation of existing hospitalization, (d) results in persistent or significant disability, (e) is a congenital anomaly or birth defect, or (f) any other AE that, based on appropriate medical judgment, may jeopardize the subject's health and may require medical or surgical intervention to prevent one of the other outcomes listed in this definition. Moderate AEs are defined as any non-serious event which causes discomfort and requires treatment, but does not pose any significant or permanent risk of harm to the participant or require in-patient hospitalization, including social or psychological trauma causing moderate or temporary distress, significant embarrassment, stigmatization of individual or community/ group, disruption of familial/social relationships or nontrivial emotional distress. Moderate AEs will include evaluation in the emergency room not leading to hospitalization. Mild is defined as any non-serious event of less than moderate severity. All SAEs and unexpected AEs will be reported to the PI or Co-Is [name] or [name] as soon as possible within 24 hours of the study staff becoming aware of the S/AE. The PI or Co-Is [name] or [name] will determine whether participation in the study should be altered or terminated for the safety of the participant.

All unexpected problems, defined as any incident, experience, or outcome that is **unexpected, related or possibly related** to participation in the research, and suggest that the research places participants are **greater risk of harm than was previously known or recognized** will be reported by the PI to the IRB and NIMH PO as soon as possible, but within 5 business days of the PI becoming aware of the AE. For all AEs and SAEs that are deemed expected and/or unrelated to the study, a summary will be submitted by the PI to the NIMH PO with the annual progress report.

Documentation of protocol deviations will begin at Visit 1 and documentation of AEs will begin once a participant begins Visit 3 and will be collected/document until the participant completes the study procedures (at the end of Visit 5) or is withdraw from the study (by self or my research staff).

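### A participant who has already taken the single capsule must be terminated if a recall visit is late, which ends later recall data and later adverse-event follow-up on randomised people

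*Combined protocol and SAP*

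**What the plan says.** All references are to the combined protocol and SAP.

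- **Termination Criteria (Protection of Human Participants, 1.a).** The lettered reasons are discretionary: staff may terminate. The window rule is not: "once a participant completes Visit 3, Visits 4 & 5 need to be completed within the above timeframe otherwise participation will be terminated". The windows are "no more than 1 week between Visits 2 & 3 and Visits 3 & 4" "and no more than 3 weeks between Visits 4 & 5".
- **Study Group Assignment.** Participants on active drug "will only receive dronabinol on one occasion". That occasion is Visit 3.
- **C.2.1 and C.2.9.** Visits 4 and 5 hold the recall tests behind the Aim 1 hypotheses. The MANCOVA takes the two recall times as a within-subject factor.
- **Data and Safety Monitoring Plan (section 5).** Staff ask about AEs at each study visit. "documentation of AEs will begin once a participant begins Visit 3 and will be collected/document until the participant completes the study procedures"; the alternative end point is withdrawal, by the participant or by research staff.
- **THC/PBO Day Measures.** A further AE review takes place about 8 hours after the capsule.
- **Visit list (Involvement of Human Participants).** Visit 5 is placed "approximately 1 week after extinction, but no more than 3 weeks later", which counts from Visit 3 and not from Visit 4.
- **Confidentiality of Breathalyzer/Drug & Pregnancy Tests.** If a participant tests positive for pregnancy or reports becoming pregnant while active, "they will be withdrawn from the study at that time". The SAE definition in section 5 includes a congenital anomaly or birth defect.

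**The concern.** A termination rule normally protects someone from further treatment. Here none remains, so what the rule ends is observation.

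Returning on time happens after randomisation. The Dronabinol paragraph under Potential Risks lists vomiting, panic attacks, anxiety and confusion among possible effects, so late return could differ between THC and placebo. If it does, removing late returners takes people out of the randomised comparison in an arm-related way. Over-enrolment to 175 replaces numbers but does not correct that.

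On safety, AE enquiry is tied to visits and stops at withdrawal. A participant who misses Visit 4 and is terminated has no scheduled enquiry after the 8-hour review. Section 5 plans formal AE comparisons, and it uses related AEs of more than mild severity as a criterion in a dosing review when about 10% of the THC group has completed. With 2 × 26 = 52 randomised to THC, that is about 5 people, so a single unrecorded event would count.

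**Working it through.** **1. Does any treatment remain when the rule applies?** The capsule is given at Visit 3. The earliest breach is a Visit 4 later than 7 days after Visit 3. No dose is scheduled after that point.

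**2. What is kept and what is lost?** I read termination under the window rule as withdrawal by research staff, because AE documentation runs "until the participant completes the study procedures (at the end of Visit 5) or is withdraw from the study" and the text includes withdrawal by staff.
- Kept: all Visit 3 measures, the 8-hour AE review, anything reported before termination, and any recall test already done. No text says that these are discarded.
- Lost: recall tests after termination, and AE documentation after termination. The plan contains no off-schedule visit, no safety contact after termination, no intention-to-treat set and no missing-data method.

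**3. Who is out of window?** Take Visit 3 as day 0 and Visit 4 on its last permitted day, day 7.
- Limit counted from Visit 4 (Termination Criteria; extinction recall test in C.2.1): 7 + 21 = day 28.
- Limit counted from extinction (visit list): day 21.

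A Visit 5 on day 24 is 24 − 7 = 17 days after Visit 4, so it is in window on the first count. It is 24 days after extinction, so it is out of window on the second. The same person is retained under one passage and terminated under the other. On the first count, a participant with no Visit 4 has no defined Visit 5 window.

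**4. How long is the AE gap?** From the earliest Visit 4 breach (day 7) to the outer limit for Visit 5 is 21 − 7 = 14 days or 28 − 7 = 21 days, depending on the anchor. Against the target schedule (Visit 5 at about day 7 or 8) the gap in calendar time is short, but the AE enquiries at Visits 4 and 5 are still lost.

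**5. The plan's own attrition figure.** 26 × (1 − 0.25) = 19.5 completers per arm, against about 20 stated. This reproduces. The documents do not split the 25% by cause, so the share due to the window rule is unknown.

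**6. Assumed worst case for bias.** Suppose that outcomes in an arm are normal and that the rule removes the poorest recallers, a fraction q, from one arm only. The mean of those left shifts by φ(z_q)/(1 − q) SD (large-sample approximation).

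| Lost of 26 | q | z_q | φ(z_q) | 1 − q | Shift (SD) |
|---|---|---|---|---|---|
| 1 | 0.0385 | −1.769 | 0.0835 | 0.9615 | 0.087 |
| 2 | 0.0769 | −1.426 | 0.1443 | 0.9231 | 0.156 |
| 3 | 0.1154 | −1.198 | 0.1946 | 0.8846 | 0.220 |

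For scale, the R61 Power Analysis names an effect of 0.72, and 0.220 / 0.72 = 0.31. These shifts bound a scenario and do not estimate the bias to expect.

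**The case against.** The other side has real points.

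- **Time-defined outcomes.** The hypotheses concern recall at 24 hours and 1 week. The windows already stretch to 1 and 3 weeks, and limiting a memory-retention test is a defensible choice. This stands, and it is why late tests should not enter the main analysis. It does not justify ending observation.
- **Visit 5 without Visit 4 is a different measurement.** Visit 4 presents all the conditioned stimuli without the snake, in both contexts, so it is itself further unreinforced exposure. This stands: such tests need a flag.
- **Pregnancy withdrawal has a purpose.** The protocol treats pregnancy as a contraindication to research MRI, and Visits 4 and 5 are normally scans. This stands. The open question is only how withdrawal, the end of AE documentation and the congenital-anomaly item fit together.

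Four stronger readings are tempting and not supported:
- A reader might infer that a terminated participant's data or whole AE record is thrown away. No passage says so; only later collection stops. Whether a participant with one recall test enters the MANCOVA is a separate missing-data question, and Hypothesis 1A accepts proximal and/or distal recall.
- A reader might infer that someone who misses Visit 4 could always do Visit 5 on time. That depends on which passage sets the anchor.
- A reader might infer that THC is known to delay return. The documents give no evidence of that; it is a possibility only.
- A reader might take 0.22 SD as the likely bias. It needs three losses, all among the poorest recallers, with no comparable loss in the other arm.

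**Conclusion.** The concern holds in a limited form. As written, the plan obliges staff to stop following randomised participants after their only dose because a visit is late, and it ends their AE documentation at the same point. No other passage repairs this. The damage is confined to recall data and AE follow-up after termination.

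The size is unknown, because the documents do not say how many participants the rule would remove or whether lateness would differ by arm. The range 0.09 to 0.22 SD rests on three assumptions: 1 to 3 losses of 26, all in one arm, and all among the poorest recallers. If losses are few, or unrelated to arm and outcome, the bias could be negligible. The AE gap does not depend on those assumptions: any participant terminated under the rule loses the later enquiries. The change is worth making because it is cheap and the lost observations cannot be recovered afterwards.

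**What to change.** 1. **Termination Criteria.** Replace termination for a missed window with a recorded protocol deviation, for PTSD and TEC participants alike, since both groups are in the same MANCOVA. Still offer the remaining recall visits if consent stands and the procedures remain permitted. Record the actual day of each test. Keep the in-window analysis as planned, and add an as-randomised sensitivity analysis that includes late tests and flags any Visit 5 done without a Visit 4.
2. **Data and Safety Monitoring Plan.** Continue AE documentation, by telephone if needed, to the planned time of Visit 5 for every participant who took a capsule, active or placebo, and has not withdrawn consent. Include those terminated by staff.
3. **Visit 5 window.** Reconcile C.2.1 and the Termination Criteria with the visit list, because the anchor decides who is out of window.
4. **Pregnancy.** Reconcile withdrawal for a reported pregnancy and the end of AE documentation at withdrawal with the congenital-anomaly item in the SAE definition.

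The cost is a short amendment, a few late visits and some telephone calls. Some tests will fall on later days, but they are confined to the sensitivity analysis. The planned analysis therefore gains no precision from late tests; the benefit is a check on selection and more complete safety follow-up.

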the overencapsulation of the required dronabinol and creation of the matching placebo. [name] will store the capsules in her office, [name], in a locked refrigerated safe. She holds current controlled substance licenses from the State of Michigan and Drug Enforcement Administration allowing her to order, store, and dispense dronabinol from her office.

[name] will randomize participants to the study groups: 5 mg dronabinol, 10 mg dronabinol, or placebo. She will dispense one pill from the appropriate container labeled by the pharmacist and put the pill into a separate pill bottle. This new pill bottle will be labeled with the participant specific ID. [name] will be responsible for appropriate documentation of drug orders, inventory, subject-specific drug order forms, dispensing, and disposal records. Research staff associated with the study will give the drug or PBO to participants, and Co-I [name]., a board-certified and licensed physician, or Co-I [name]., a board-certified and licensed psychiatrist, or their physician designate, will be present on-site and/or available by pager/phone.

b. Sources of Materials

Primary Diagnostic Assessments (Table 1)

(1) Mini International Neuropsychiatric Interview Version 6.0.0 (MINI): The MINI is a structured interview for general diagnostic assessment providing an assessment of major psychiatric diagnoses; (2) Clinician-Administered PTSD Scale for DSM-5 (CAPS-5)¹⁵⁴, a validated, gold-standard clinician interview measure of PTSD severity. WSU clinical research staff members will conduct diagnostic interviews using MINI/CAPS instruments. While most interviews will be conducted by one rater, inter-rater reliability will be examined to ensure good reliability (Kappa at least 0.6)¹⁵⁵.

Table 1: R61 Assessment Schedule

	Screening, Informed Consent, & Study Entry	Fear Acquisition	fMRI			
			THC or PBO	Fear Extinction	Extinction Recall Test 1	Extinction Recall Test 2
MINI	✓					
CAPS-5	✓					
Standard Health Questionnaire	✓					
Ethnicity/Race Form	✓					
MRI Safety Form	✓					
Gender Identity Questionnaire	✓					
Concomitant Medication Form	✓					
Handedness Questionnaire	✓					
Connor-Davidson Resilience Scale	✓					
Posttraumatic Growth Inventory	✓					
LEC-5	✓					
PCL-5	✓					
PSQI	✓					
STAI**	✓			✓		
HAM-D	✓					
HAM-A	✓					
BDI-II	✓					
C-SSRS	✓					
WHODAS 2.0	✓					
CTQ	✓					
ERQ	✓					
ACQ	✓					
US Expectancy		✓	✓	✓	✓	✓
SUDS		✓	✓	✓	✓	✓
VAS**			✓			

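### The trial is declared double-blind, but the written procedure has one person, apparently the PI, randomise to content-named arms and pick the matching capsule, with no coded labels or separately held key described

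*Combined protocol and SAP*

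**What the plan says.** C.2 Overall Study Design calls the trial randomised, double-blind and placebo-controlled. Allocation is covariate-adaptive: each new assignment depends on baseline characteristics and on the assignments already made. Study Group Assignment adds: "All capsules will be administered to participants in double-blind conditions". The capsules are opaque and the placebo looks identical. The Dronabinol paragraph under Potential Risks says that blinding has to be kept even at debriefing.

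Study Group Assignment also sets out the handling of the capsules:

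- "Study medication, dronabinol or PBO, will be dispensed to participants by PI", who holds a controlled-substance research licence.
- A pharmacist over-encapsulates the drug and makes the matching placebo.
- A person whose name is removed stores the capsules in her office. On licensing, the text reads: "She holds current controlled substance licenses from the State of Michigan and Drug Enforcement Administration".
- A person whose name is removed "will randomize participants to the study groups: 5 mg dronabinol, 10 mg dronabinol, or placebo".
- The dispensing step follows, by the same woman as the text reads: "She will dispense one pill from the appropriate container labeled by the pharmacist and put the pill into a separate pill bottle".
- On how the second bottle is marked, the plan adds: "This new pill bottle will be labeled with the participant specific ID".
- Handing over the capsule falls to others: "Research staff associated with the study will give the drug or PBO to participants".

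Other sections give the PI further roles. The PI or a Co-I reviews the health information (Medical and Neurological Health Determination). The PI or Co-Is decide whether participation is altered or ended after serious or unexpected adverse events (5. Data and Safety Monitoring Plan). The PI and the coordinator oversee data integrity, safety monitoring and adverse-event reporting (Reporting responsibility).

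**The concern.** Someone who assigns a participant to a named dose or to placebo, and then selects the container for that arm, knows the allocation unless both the allocation result and the stock labels are coded. The plan describes neither. If that person is the PI, two protections weaken. The first is allocation concealment: she knows earlier assignments, the scheme uses earlier assignments, and she may be the one who passes a candidate as medically fit. The second is masking after randomisation: she may decide who stays in the study after certain adverse events, and she shares oversight of data and safety. A trial reported as double-blind should be able to say which roles were blind, and this text does not allow that.

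**Working it through.** The point has no formula. It rests on setting the passages side by side.

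1. **Is the randomiser the PI?** One paragraph of Study Group Assignment says the PI dispenses and holds State of Michigan and DEA licensing. The next describes a woman with State of Michigan and DEA licences who stores and dispenses the capsules. The roles and licences match. This is a strong inference, not a stated fact, because the name is removed.

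2. **Does the procedure reveal the arm?** The groups are listed by content, and the capsule comes from whichever container fits the assigned group. To choose it she must know which container belongs to which assignment. Coded container labels alone would not mask her if she also receives the assignment as a named arm; the allocation result would have to be coded too.

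3. **Is any safeguard described elsewhere?** No section on randomisation, dispensing, labelling, blinding or adverse-event assessment mentions coded stock labels, a coded allocation result, a separately held key or an independent unblinded dispenser.

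4. **Who appears masked?** Participants receive identical opaque capsules. The staff who hand them over receive a bottle marked with the participant ID. Both appear masked.

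5. **Which PI roles involve judgement?**
   - Medical and neurological eligibility review, which a Co-I may do instead.
   - Participation decisions after serious or unexpected adverse events, which Co-Is may make instead.
   - Oversight of data integrity and safety monitoring, shared with the coordinator.

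6. **Which roles are not the PI's?** For diagnostic eligibility, "WSU clinical research staff members will conduct diagnostic interviews using MINI/CAPS instruments". Suicidal ideation is evaluated at the initial assessment and Table 1 schedules the C-SSRS only at screening, before randomisation at Visit 2, so removal on that ground is not counted here.

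7. **How many participants pass through the step?** Three arms of 26 give 3 × 26 = 78 planned PTSD participants. The plan allows enrolment of up to 175 overall, so the number randomised could differ.

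**The case against.** The strongest reply is that this is silence rather than contradiction. The plan says only that the pharmacist labels the containers, not what the labels say, and a sentence listing the study groups need not show what the dispenser sees. That stands in part: the text does not prove that the PI is unblinded. But the procedure as written has the same person assign and select. A reader following it would arrive at an unblinded dispenser, so a safeguard that exists should be stated.

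The second reply is that the Aim 1 measures are protected. That stands. BOLD and SCR are instrument-recorded, and SUDS and US expectancy are self-reports by participants who appear masked.

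Some stronger readings are tempting, and the documents do not support them:

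- A reader might infer that the PI could shape the analysed sample through the reference to usable fMRI and SCR data. That phrase is in the R61 Power Analysis. It is a planning assumption about completers and defines no analysis set.
- A reader might infer that one relatedness rating could decide the early safety criterion. The criterion compares THC with placebo, and the result is an amendment request, so a single rating need not settle it.
- A reader might infer that the PI rates adverse events. Study personnel collect and log them, no relatedness rater is named, and Co-Is are consulted on grading. The events are only brought to the PI's attention. What remains is that no rater is said to be masked.
- A reader might infer that she can predict the next assignment. Neither the random element nor the covariate weights are given, and Visit 2 may fall up to 6 months after Visit 1, with others randomised in between. Any figure for predictability would be an assumption.

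**Conclusion.** The concern holds as a gap between a declared property and a described procedure. Followed as written, the procedure costs the trial allocation concealment and the masking of the PI in the eligibility review, in participation decisions after adverse events, and in data and safety oversight. This rests on two assumptions: that the unnamed randomiser is the PI, which is strongly indicated, and that no coding exists beyond what is described, which the text leaves open. The step covers every randomised participant, 78 as planned. The size of any bias cannot be derived, and no bias in the scoring of the main outcomes is claimed. The change is worth making because it is cheap and removes the doubt.

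**What to change.** Preferred: the pharmacist applies code labels when preparing the capsules, and holds the arm key and the records that reveal content. The allocation step returns only a code, so the PI can store and dispense without seeing the arm. The pharmacist, or a system the PI cannot view by arm, would then hold the previous assignments that the adaptive scheme needs, and the present assignment of drug records would have to be reworded.

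Alternative: declare the PI unblinded. Have the medical eligibility review, already open to a Co-I, and the adverse-event relatedness ratings made by Co-Is kept unaware of allocation. Leave the safety-removal rules as they are. This option discloses the PI's knowledge in those decisions but does not remove it.

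In either case, state which roles are blinded, whether the stock labels are coded, and who holds the allocation list.

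The cost should be a little pharmacist time for the first option, or a little Co-I time for the second. The documents give no figures for either. Both use people already in the plan and add no visits.
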